## 6 Treatment of Participants

### 6.1 Description and justification for treatments, interventions or methods to be utilised

All participants will receive the investigational oral insulin (Capsulin) for the duration of 12w. They will first be commenced on 150 IU Capsulin for one week. They will then have their dose increased to the therapeutic dose of 300 IU (150 IU twice daily) for the remaining study duration.

### 6.2 Permitted medications/treatments

All participants will be on either the 670G or 770G Hybrid Closed Loop insulin regimen. They will continue on this regimen throughout the study duration.

### 6.3 Monitoring of participant compliance

All participants will be provided the Capsulin in bottles fitted with Aardex track cap. Adherence with the dosing schedule will be determined from the Aardex history and from the number of capsules remaining in the bottles when participants attend their clinical reviews and the final visit. Participants self-reporting of adherence will also be recorded.

## 7 Assessment of Efficacy

### 7.1 Outcomes

1. Total insulin dose (units/kg/day) and the proportion of basal and bolus insulin
2. CGM metrics (13): 12-week CGM data will be collected for variables: Mean SG, % time in range 3.9 to 10 mmol/l, % time in hypoglycaemia (< 3 and < 3.9 mmol/l), % time in hyperglycaemia (>10 and >13.9 mmol/l), and glycaemic variability (coefficient of variation and standard deviation)
3. Auxology: Body mass index Z-scores
4. Metabolic bloods: Lipid profile (Triglycerides, cholesterol, LDL and HDL), Liver function test, HbA1c
5. Gut hormone (glucagon, glucagon-like polypeptide-1 (GLP-1) and glucose-dependent insulinotropic polypeptide (GIP)) responses to a standard meal challenge
6. Safety (Adverse events, Severe adverse events: Severe hypoglycaemia, diabetes ketoacidosis)
7. Recruitment and retention rates
8. Adherence to medication (track caps)
9. Patient-reported outcomes: experiences with oral insulin on appetite, GI disturbances and glycaemic outcomes

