## 2 Rationale / Background

### 2.1 Background summary

Replacement of exogenous insulin is critical in the management of T1D. However, this replacement requires subcutaneous insulin delivery, either as multiple daily insulin injections or by continuous insulin infusion through an insulin pump. Despite advancements in monitoring and improved delivery systems, more than three quarters of people with T1D are not able to achieve optimal glycaemic control (1). Administration of insulin remains a relatively invasive process and is not the most convenient form of

delivery; hence, engagement with insulin administration may be sub-optimal. Oral insulin, however, may be perceived as a more attractive form of insulin delivery, although this has remained an elusive goal. In addition to the ease of administration with an oral preparation, the more significant advantage lies in the different pharmacokinetics having an ability to replicate a near-physiological state, closely mimicking the portal delivery of endogenous insulin. Oral insulin is absorbed by the gastrointestinal tract with its action at the liver, the primary organ of glycaemic control (high portal insulin and low peripheral insulin levels), whereas subcutaneous injections induce high systemic insulin levels, with greater risk of hypoglycaemia and weight gain. Oral insulin, by reducing systemic insulin levels, has the potential to minimise hypoglycaemia, weight gain and may also restore  $\beta$  cell function by reducing the immune response in tissues (2). The multiple perceived benefits of oral insulin delivery have led to various formulations of oral insulin, currently limited to small clinical studies (3).

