### 4.2 Study Design

The proposed pilot study is a prospective, 12-week single-arm observational study in 10 adolescents/adults with T1D in Western Australia. The study design is shown in Figure 2, below:

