#### **4.8 Trial Duration/Schedule**

Expected duration of the study is 12 months. Each participant's time in the study is 12 weeks. The visits, assessments and visit duration for every participant is listed in the table below.

Visit Sequence	Visit Duration	Assessments	Comment
VISIT 1 (Week0)  STUDY START	8.5h	Informed Consent confirmed.	
		Height, weight, BP, Date of Birth, Date of Diagnosis, Date of pump start, Date of start of closed loop  Pump download for pump settings and CGM data	Ensure participants are well and that the prior two weeks representative of routine diabetes management
		Glycaemic measures: HbA1c, total insulin dose, insulin sensitivity factors, insulin-carbohydrate ratios and CGM metrics	
		Metabolic measures (2mls blood): lipid profile, liver function tests	Fasting bloods
		Meal Challenge (following an overnight fast) with standard SC pre-meal bolus via pump.  Measure gut hormone responses over 5h - plasma GLP-1 (glucagon like peptide), GIP (glucose dependent insulinotropic polypeptide), plasma glucagon and free insulin.  A total of 106 mls will be drawn for 15minutely blood BGL testing and gut hormones during the meal challenge.	SC bolus to be administered for standard meal. Meal is to be eaten within 20 minutes under supervision. No other oral intake (excluding water) for the next five hours.
		Dexcom G6 set-up and training for those on 670G. Provided with sufficient sensors for 2 weeks .	As Medtronic 670G users do not have the follow-function (available with 770G), participants using 670G will be offered an additional continuous glucose monitor (Dexcom G6) to obtain glucose data during the first three weeks of the study period. The device has a share function which will permit the research staff to review the glucose levels in real-time.
	Participants are commenced on once daily dose of 150 IU	Participants will be commenced on oral	

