		
Capsulin, at the end of the meal challenge. They are provided with lunch half an hour after the oral insulin dosing, and observed for a further 2h prior to discharge.
 
Participants are educated on the appropriate timing of the oral insulin dosing: Capsulin is to be taken half an hour before a main meal.
 
Review home hypoglycaemia management with participant &/or parent. Provide oral insulin for a week
	
insulin 150 IU OD, to ensure stability of the closed loop algorithm. Dose increased to 150 IU BD after one week
 
As per ISPAD & Diabetes Australia guidelines.

VISIT 2 (Week 1)	1.5h	Clinical review of total insulin dose, insulin sensitivity factors, insulin-carbohydrate ratios and CGM metrics.	
		Assessment of Capsulin use, and adverse events	Review of logbook and Aardex history
		Commenced on twice daily 150 IU Capsulin– with appropriate education of use. Provide oral insulin for 5 weeks	
VISIT 3 (Week 6)	45 min	Pump download for pump settings and CGM data. Clinical review of total insulin dose, insulin sensitivity factors, insulin-carbohydrate ratios and CGM metrics.	
		Assessment of Capsulin use, and adverse events	Review of logbook and Aardex history
		Provided with further Capsulin for remaining 6w; twice daily 150 IU dose. Participants are educated on the appropriate timing of the oral insulin dosing: Capsulin is to be taken half an hour before two main meals.	
		Participant to return Dexcom G6 transmitter to researcher	
VISIT 4 (week 12) (STUDY END)	6.5h	Height, weight, BP,	
		
Pump download for pump settings and CGM data
 
Glycaemic measures: HbA1c, total insulin dose, insulin sensitivity factors,
	

		insulin-carbohydrate ratios and CGM metrics	
		Metabolic measures (2mls blood): lipid profile, liver function tests	Fasting bloods
		Meal Challenge (following an overnight fast) with an oral insulin pre-meal bolus. Measure gut hormone responses over 5h - plasma GLP-1 (glucagon like peptide), GIP (glucose dependent insulinotropic polypeptide), plasma glucagon and free insulin. A total of 106 mls will be drawn for 15minutely blood BGL testing and gut hormones during the meal challenge.	
		Participant report of outcomes determined – Appetite and impact on dietary intake, perceived weight loss and well-being.	
VISIT 5 (14w)	30 min	Pump download for pump settings and CGM data	This visit is to ensure that participants are back on baseline therapy.

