#### 5.2 Participant inclusion criteria.

1. T1D of at least 1 year duration,
2. C-peptide < 0.1nmol/l (in the absence of hypoglycaemia)
3. Age 16 - 25 years
4. On Medtronic 670G/770G (using closed loop system for  $\geq 70\%$  of the time in last 2 weeks)
  - No plans to change the management during the study period.
5. HbA1c < 7.5%
6. Ready to meet the requirements of the protocol.
7. Has the ability to download the insulin pump if on Medtronic 670G (Medtronic 770G users have automatic download)
8. English speaking, living in an area with internet and cellular phone coverage

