### 7.2 Efficacy assessment

The methods and timing for assessing, recording, and analysing efficacy parameters:

- Insulin profiles and CGM metrics will be assessed at each clinical review – Visit 1,2,3,4. They will also be monitored weekly using the Medtronic and Dexcom databases.
- Other clinical & metabolic outcomes will be measured at study start and study end – Visit 1 & 4
- Adherence to medication and adverse events will be determined at each clinical review – Visit 1,2,3,4
- Patient self-reported outcomes will be determined at the end of the study duration by means of a questionnaire

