#### **9.5 Selection of participants for analyses:**

All participants who have complete data for the 12w study duration – including adherence to the study drug, insulin profiles, CGM metrics, clinical and metabolic outcome measures; will be included in the analyses.

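### BMI Z-score is the only listed body-size outcome although participants may be up to 25 years old; change in weight and BMI should be listed for everyone

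*Protocol*

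**What the plan says.** Section 7.1 lists nine outcomes. The body-size entry reads in full "Auxology: Body mass index Z-scores"; neither weight nor BMI itself appears in the list. Section 5.2 sets eligibility at "Age 16 - 25 years", and section 4.2 describes a "12-week single-arm observational study in 10 adolescents/adults with T1D in Western Australia".

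The visit table in section 4.8 records "Height, weight, BP, Date of Birth, Date of Diagnosis" at Visit 1 and "Height, weight, BP" again at Visit 4 (week 12). Section 7.2 agrees: "Other clinical & metabolic outcomes will be measured at study start and study end".

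Section 2.1 gives the reason for looking at weight. Oral insulin "has the potential to minimise hypoglycaemia, weight gain", and an earlier 10-day study in type 2 diabetes is cited as showing a small fall in weight. At Visit 4 participants are asked about weight loss as they perceive it. Section 9.1 promises the mean, SD and 95% confidence interval of the paired change for continuous outcomes.

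The protocol states no growth reference, upper age limit or rule for adults.

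**The concern.** A BMI Z-score is defined only relative to a reference population of the same age and sex. The sample runs from 16 to 25 years, so the measure may not cover all of it. A participant older than the reference has either no score or one obtained by a convention, for instance scoring everyone above the limit as if they were at the limit.

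This goes beyond a detail that a statistical analysis plan would settle. Such a plan could name the reference and the convention, but the protocol itself chose the metric as the sole body-size outcome, and naming a reference does not extend its age range.

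At stake is how readable one secondary result will be. A pilot meant to inform a larger trial should report weight change on a scale that means the same for every participant. The plan records perceived weight loss but does not list measured weight change as an outcome.

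**Working it through.** The protocol gives no figure on this point, so there is nothing to reproduce. Three illustrative checks follow.

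**Inputs from the protocol.** Ages 16 to 25 (section 5.2); N = 10 (section 9.1); height and weight at Visits 1 and 4 (section 4.8).

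**Assumptions.** The reference's upper age limit U is not stated, so it is varied from 18 to 23 years. Ages are taken as evenly spread from 16 up to the 26th birthday.

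**1. How many participants lie beyond the reference.** The expected share is p = (26 − U)/10, and the chance that at least one of 10 is affected is 1 − (1 − p)^10.

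| U (years) | p | Expected beyond, of 10 | Expected within | Chance of at least one beyond |
|---|---|---|---|---|
| 18 | 0.8 | 8 | 2 | >99.9% |
| 19 | 0.7 | 7 | 3 | >99.9% |
| 20 | 0.6 | 6 | 4 | >99.9% |
| 21 | 0.5 | 5 | 5 | 99.9% |
| 23 | 0.3 | 3 | 7 | 1 − 0.7^10 = 97.2% |

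**2. If the Z-score is reported only where it is defined.** The half-width of the 95% confidence interval for a mean paired change, in units of the SD of that change, is t(0.975; n − 1)/√n.

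| n with a score | Half-width (SDs) |
|---|---|
| 10 (everyone) | 0.72 |
| 7 | 0.92 |
| 5 | 1.24 |
| 4 | 1.59 |
| 3 | 2.48 |
| 2 | 8.98 |

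With 7 scores the estimate is somewhat less precise than with 10. With 2 it is uninformative.

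**3. If everyone is scored with the age held at the limit.** Take the usual form Z = [(BMI/M)^L − 1]/(L·S). Assumed parameters are M = 21 to 23 kg/m², S = 0.12 to 0.18, L = −2 or −1.5, and height 1.70 m. A loss of 1 kg lowers BMI by 1/1.70² = 0.346 kg/m².

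Worked case with M = 22, S = 0.15, L = −2:

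- Starting BMI 22: [(21.654/22)^−2 − (22/22)^−2]/(−0.30) = (1.0322 − 1)/(−0.30) = −0.107.
- Starting BMI 27: [(26.654/22)^−2 − (27/22)^−2]/(−0.30) = (0.6813 − 0.6639)/(−0.30) = −0.058.

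Over the whole grid, 1 kg lost moves Z by −0.044 to −0.147. The sign is always kept. For small changes the ratio between starting BMI 22 and 27 is (27/22)^(1 − L), which is 1.67 for L = −1.5 and 1.85 for L = −2. The same loss in kg therefore counts for nearly twice as much in the lighter participant.

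Change in kg and in kg/m² needs no reference and is available for everyone seen at both visits.

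**The case against.** The strongest reply is that nothing is lost. Height and weight are taken from everyone at Visits 1 and 4, and section 7.1 expresses insulin dose per kg, so weight must be in the data set anyway. Change in kg and BMI, with its SD, can be computed at any time. This stands. A reader might infer that the weight effect will be missing, or that the later trial will have no usable SD; the protocol supports neither. The SD that section 9.1 singles out, with an upper one-sided 80% limit, is for the change in daily subcutaneous insulin.

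Weight is also a modest part of the plan. Section 2.1 speaks of a potential, the hypothesis in section 3 concerns insulin dose, and no weight change of any size is predicted. It would overstate the text to say that the protocol expects a weight effect.

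A reader might further infer from section 9.5, where participants complete on "clinical and metabolic outcome measures; will be included in the analyses", that an adult without a Z-score would be dropped. That is only one possible reading. Someone measured at both visits has supplied the data, and nothing says that a derived score outside a reference's range makes that person incomplete.

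Finally, an age-referenced score is reasonable for 16- and 17-year-olds, a reference could reach further into adulthood than 18 to 20 years, and a fixed-age convention preserves the direction of change. All of this limits the size of the point. It does not make the Z-score a suitable sole measure for a sample running to 25.

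**Conclusion.** The point holds as a minor flaw in an outcome definition. The only listed body-size outcome is a score that may be undefined, or depend on an unstated convention, for part of the eligible age range. Its mean change and SD would be hard to interpret as a weight effect.

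The expected number affected is 3 of 10 for a reference ending at 23 years and 8 of 10 for one ending at 18. These figures rest on an assumed age limit and on even recruitment, so no single percentage should be quoted as the size. The scale effect in the third check also rests on assumed reference parameters. Distortion is possible rather than certain, since it depends on a reference and convention that the protocol does not fix.

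The primary outcome, the sample size of 10 and the data to be collected are unaffected.

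**What to change.** In section 7.1, make the auxology outcome the change in weight (kg) and in BMI (kg/m²) from Visit 1 to Visit 4 for all participants, summarised as section 9.1 already provides for continuous outcomes. Keep BMI Z-score only as a supplementary description, restricted to participants within the age range of a reference that is named.

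The cost is a change of wording. No new measurement, visit or participant is needed, because height and weight are already recorded at both visits.

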improvement in the lipid profile with 10% improvement in LDL and total cholesterol and 20% for triglycerides. These promising findings open up avenues to explore the potential of oral insulin in people with T1D.

*Proposed Study:* This pilot study will expand on the findings from these previous studies by exploring the utility of oral insulin in individuals with T1D over a 12-week period.

The proposed study aims to provide preliminary data of whether oral insulin is acceptable and can be used as an adjunct therapeutic intervention in individuals with T1D, and to use the information obtained to inform a future randomised controlled trial specifically designed to assess the efficacy of oral insulin as an adjunct to current insulin therapy. The 12-week study will provide sufficient duration to review glycaemic outcomes that can be measured by HbA1c and metrics from continuous glucose monitoring (CGM) which include time in hypoglycaemia, time in target glucose range and time in hyperglycaemia. We predict a reduction in total subcutaneous insulin dose with supplemental oral insulin will lead to a reduction of systemic hyperinsulinemia. This in turn, has the potential to further reduce hypoglycaemia, which still remains a concern in individuals with T1D (9, 10). This study will also enable us to explore trends of glycaemic variability with daily oral insulin therapy. Improvement in these glycaemic measures are known to reduce the long-term risk of diabetes macro and microvascular complications (11, 12). Liver is the primary site of insulin delivery with oral insulin, unlike subcutaneous insulin, where systemic insulin levels are high in target organs which include liver, muscle and adipose tissue. Hence, the study will also review metabolic parameters with the potential role of oral insulin being cardio-protective.

Our ultimate aim is to improve our understanding of oral insulin and make recommendations for future research to enhance improvements in clinical care to better support people with T1D.

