## 8.4 Adverse event reporting

Capsulin has been used effectively in type 2 diabetes management with no adverse outcomes. Further, as all participants are on hybrid-closed loop therapy, whereby the patient's insulin settings are adjusted on a 24h basis, minimal risks are expected during this study. Similarly, the risk of a serious adverse event is low. Any serious adverse event will be reported to Child Adolescent Health Service Human Research Ethics Committee using the Initial Serious Adverse Event Report Form within 72 hours of the event occurring or 24 hours if there is a material impact on the ethical acceptability of the study as considered by the principal investigator.

Adverse events will be elicited at each clinical review by means of clinician assessment and reviewing of the participant Logbooks. Further participants CGM and pump uploads are reviewed on a weekly basis for early pick-up of adverse events.

Adverse events are defined as:

- Gastrointestinal disturbances
- Skin rashes following oral insulin therapy and not related to pump/sensor therapy
- More than 40% increase in hypoglycaemia from baseline
- Hyperglycaemia with ketosis

Severe adverse events are defined as:

1. Severe hypoglycaemia: coma/convulsion/any episode requiring third party assistance for hypo treatment
2. Severe diabetic ketoacidosis: (venous pH < 7.2)
3. Any in-patient hospitalisation

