# 9 Data Management, Statistical Analysis and Record Keeping

## 9.1 Statistics and Interim Analysis

This will be a pilot study with 10 participants. This sample size was chosen based on providing estimates of the mean and variance of outcome measures to within a degree of precision acceptable to inform the power calculation for a definitive trial. Appropriate descriptive statistics (frequencies (%), mean (SD), median (IQR)) will be presented for all sociodemographic and clinical characteristics of the sample. Mean and standard deviation, along with their 95% confidence interval, will be presented for continuous/interval outcome measures of interest in each phase and for the paired difference between baseline and end of study. The SD for the primary outcome (change in average total daily insulin delivered subcutaneously) will be presented along with the upper value of a one-sided 80% confidence interval.

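### Liver function tests are placed outside Safety and outside the adverse-event definition, so a symptomless enzyme rise in up to 3 of 10 participants would show only as a mean change whose 95% CI includes zero

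*Protocol*

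**What the plan says.** Section 3 asks whether oral insulin is both effective and safe as an add-on treatment. Section 2.1 states: "Liver is the primary site of insulin delivery with oral insulin". Section 5.3 excludes people with active liver disease. Liver function is tested at Visits 1 and 4 only (sections 4.8 and 7.2).

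Section 7.1 puts the result in item 4: "Metabolic bloods: Lipid profile (Triglycerides, cholesterol, LDL and HDL), Liver function test, HbA1c". Item 6 reads "Safety (Adverse events, Severe adverse events: Severe hypoglycaemia, diabetes ketoacidosis" and contains no laboratory measure. The visit table in section 4.8 also labels liver tests as metabolic.

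Section 8.4 introduces its list with "Adverse events are defined as" and names four events: gut symptoms, drug-related rash, hypoglycaemia up by more than 40% on baseline, and high glucose with ketosis. Severe events are severe hypoglycaemia, severe ketoacidosis and any hospital admission. Events are found through clinician assessment, logbooks, and sensor and pump uploads. Follow-up under section 8.5 begins from an adverse event.

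On analysis, section 9.1 says: "Mean and standard deviation, along with their 95% confidence interval, will be presented for continuous/interval outcome measures of interest in each phase", and likewise "for the paired difference between baseline and end of study". Frequencies and medians are named for a different purpose: "median (IQR)) will be presented for all sociodemographic and clinical characteristics of the sample".

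**The concern.** Possible liver harm shows in individual values outside the laboratory range, not in a group average. The protocol collects the values that could reveal it, but two of its own provisions keep them out of safety reporting: the outcome list treats them as metabolic, and the adverse-event list, worded as a definition, has no entry that a symptomless enzyme rise could meet. What remains is a group mean of 10, in which a few large rises raise the mean a little and the SD a great deal.

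At stake is whether the pilot can answer the safety part of its question for the liver, and whether the planned randomised trial inherits a usable signal or only a mean with a wide interval.

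**Working it through.** **The plan's own figure.** Section 9.1 states: "This will be a pilot study with 10 participants". No effect size, SD, power or precision target is given, so 10 cannot be reproduced. It does fix the precision: with 9 degrees of freedom the two-sided 95% critical value is t = 2.262, and the CI half-width for a mean change is 2.262/√10 = 0.715 SD.

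**Does a symptomless rise meet section 8.4?** None of the four listed events is a laboratory finding. Of the three severe events, only hospital admission could capture it. Without symptoms or admission, it meets neither definition.

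**What would the section 9.1 summary show?** The protocol gives no enzyme values, so assume that k of n = 10 participants rise by X and the rest do not change. Then

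- mean change = kX/n
- SD = X·√[k(n−k)/(n(n−1))]
- t = mean/(SD/√n) = √[k(n−1)/(n−k)] = √[9k/(10−k)]

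X cancels from t, so whether the CI includes zero does not depend on the size of the rise. The last three columns take X = 100 U/L as an illustration.

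| k | t | p | Mean change | SD | 95% CI |
|---|---|---|---|---|---|
| 1 | 1.00 | 0.34 | +10 | 31.6 | −12.6 to 32.6 |
| 2 | 1.50 | 0.17 | +20 | 42.2 | −10.2 to 50.2 |
| 3 | 1.96 | 0.081 | +30 | 48.3 | −4.6 to 64.6 |
| 4 | 2.45 | 0.037 | +40 | 51.6 | 3.1 to 76.9 |

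The interval first excludes zero at four of 10.

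**Sensitivity to the assumptions.**

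- Unequal rises in three participants: 60, 100 and 180 U/L give mean 34, SD 61.9, CI −10.3 to 78.3. Rises of 100, 180 and 380 U/L give mean 66, SD 126.2, CI −24.2 to 156.2. Both include zero.
- Random change added for every participant (assumed SD 3 to 8 U/L; rises of 100 or 180 U/L; 100,000 draws per scenario): the CI included zero in all draws, to the accuracy printed, for one or two affected. For three affected it did so in 94% to 100% of draws.

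**What a count would show.** One of 10 newly above range is 10% (exact 95% CI 0.3% to 44.5%). Three of 10 is 30% (6.7% to 65.2%). None of 10 would still leave an upper limit of 30.8%. The count is also imprecise, but it shows that affected individuals exist and how many.

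**The case against.** The other side has several good points.

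- **A reader might infer that such rises would be reported as no change.** The documents do not support that. Section 9.1 prints mean, SD and 95% CI and sets no test or decision rule for liver tests. Three rises of 100 U/L would be printed as +30 with SD 48.3, which an attentive reader would question. An interval that includes zero is not a finding of no effect.
- **A reader might infer that liver tests may be summarised only in this way.** Section 9.1 does not say so and excludes no listing or count. A statistical analysis plan, not available here, may add individual summaries. Their absence from the protocol is not in itself a fault.
- **A reader might infer that no liver event could ever be recorded.** Hospital admission would make it a severe event. The monitoring board receives accruing data (section 8.3), and the side-effects to be watched in section 8.1 are given as examples.
- **The metabolic label has a rationale.** The section 2.1 statement about the liver leads to an interest in metabolic and cardiovascular benefit, and section 8 describes no liver risk.
- **The arithmetic is general.** It applies to any mean of 10 and is not evidence of liver effects in this trial.

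What remains is the classification in section 7.1 and the definition in section 8.4. Both are protocol content that an analysis plan would not normally rewrite. The board is directed to safety outcome measures, and liver tests are not listed as one. The section 8.4 list is also incomplete on the protocol's own terms: headache is monitored under section 8.1 but is absent from it.

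**Conclusion.** The point holds in a limited form. Sections 7.1 and 8.4 place liver tests outside safety, and a symptomless enzyme rise without admission would not meet the adverse-event definition. In the summary that the protocol describes, it would appear as a positive mean change with an inflated SD and without identifying who was affected. With equal rises in up to three of 10 and no change in the others, the 95% CI includes zero whatever the size of the rise.

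The interval result rests on the assumed pattern of a few risers among stable participants. At three affected it is close to the boundary (1.96 against 2.262), so random variation occasionally moves the lower limit above zero. The finding on the adverse-event definition needs no assumed values and is the stronger half. The summary half is weaker, because an analysis plan could already add individual reporting. The change is worth making, but the point does not undermine the trial's primary aim.

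**What to change.** 1. **Section 7.1:** list liver function tests under item 6 (Safety) as well as item 4, which keeps the metabolic purpose.
2. **Section 9.1 or the analysis plan:** report each participant's baseline and week-12 values relative to the laboratory's upper limit of normal, with the number newly above range. Keep mean (SD, 95% CI) as an additional line.
3. **Section 8.4:** reword the list so that it is not exhaustive and a new out-of-range liver result can be recorded as an adverse event when the study doctor judges it clinically significant. No management threshold is proposed.

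Clinical judgement is preferable to logging every above-range value automatically. If one assumes six independent analytes, each above range in 2.5% of healthy people, the chance of at least one is 1 − 0.975⁶ = 0.14, or about 1.4 of 10 participants at week 12. This is an upper illustration, since correlation within a person reduces new crossings.

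The cost is protocol wording, one small table from blood already drawn, and possibly a few logged events of little importance. One limit remains: liver tests are scheduled only at Visits 1 and 4, so a participant who stops early has no planned second value to tabulate.
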